To conduct a pilot feasibility RCT among up to 48 women, either diagnosed with GDM and referred to the High Risk Obstetric Consultants (HiROC) at the University of Tennessee Medical Center Knoxville (UTMC), or at risk for GDM (e.g., failed the 50g, 1-hr screening test) and managed by one of the clinics listed in Section J. The RCT will compare a physical activity (behavior change) intervention (i.e., walking/stepping in place) versus a general wellness intervention (i.e., health education focusing on immunizations, contraceptive options following delivery, etc.) on PA levels, maternal glycemic profile in the third trimester, and infant size and anthropometrics (i.e., weight, length, head, abdominal and upper mid-arm circumference, and skinfolds at the flank, thigh, triceps, bicep and subscapular).

It is hypothesized that the PA intervention will increase PA levels during pregnancy, and improve maternal glycemic profile in the third trimester and infant anthropometric measures at birth. The exploratory hypothesis is that improvements in third trimester glycemic profile mediate the effect of pregnancy PA on the infant anthropometric measures.

C. Study Staff

Student research assistants working on the study (i.e., recruitment, conducting intervention sessions and data assessment visits) will be trained and overseen by Drs. [name] and [name]. All will remain up to date on required IRB trainings and approvals (e.g., CITI trainings and UTMC outside learner approval) for the duration of their work on the study.

D. Usual Care

Usual care at HiROC for women with GDM includes bimonthly to weekly in-person appointments, depending on the patients' needs and adherence to the diabetes

educators' recommendations, to monitor their capillary glucose levels, provide counseling on diet, and prescribe or adjust medications, as needed. PA is usually encouraged at the first GDM appointment, but is not directly prescribed, further discussed or typically tracked in conjunction with usual clinical care. Women at risk for GDM (i.e., who fail the screening but not the diagnostic test), are not seen by HiROC for diabetes education.

E. Data Assessment Overview: The Project Wellness Study Visits

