Study staff will make photocopies of the capillary blood glucose values recorded for HiROC clinical care (i.e., between the first new GDM appointment and the follow-up GDM visit one week later, these are recorded in the HiROC purple self-monitoring booklet distributed to all new GDM patients) to supplement the Study Visit 1 data, for women with GDM only. For all participants, all prepregnancy and pregnancy weights, and height, will be abstracted from the medical records, as will the results of all blood glucose testing during pregnancy.

Participants will not be randomized until all elements of Study Visit 1 have been completed (i.e., surveys and FFQ, PAM, PAM diary log, CGM) and received by study staff. These elements must be completed and received by 30 weeks 6 days gestation in order to be randomized.

M. Randomization

Participants will be randomized to one of the two interventions upon completion of the Study Visit 1 data assessment; they will be contacted by text message and/or ultimately by telephone, by their interventionist, to learn the group they are assigned to and

schedule the initial intervention session (described below). We plan to recruit and enroll up to 48 participants so that we may randomize at least up to 36. Randomization will be stratified for at risk for GDM vs. diagnosed with GDM (split evenly between strata). We will utilize block randomization (to ensure equal sample sizes), with a block size of 4. The allocation sequence will be managed by [name] (UTK, Public Health) and concealed from the study intervention staff until it is needed. Intervention staff will contact the participants to inform them of their assigned intervention condition and schedule the initial intervention session (at < 31 weeks 6 days gestation).

N. Study Visit 2 (Follow-up Data Assessment, Study Visit ≤ 36 weeks gestation)

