On the Study Visit 1 in-person survey, participants will be asked if they are interested in participating in the optional delivery visit. If so, they will be asked to provide the names and telephone numbers of 1-2 individuals who plan to be with them at the delivery and to give study staff permission to contact those individuals to help schedule the newborn infant measurements. Participants will be asked to update this information, if it has changed, at Study Visit 2 in-person survey. Study staff will check in with those individuals by text every few days around the woman's estimated delivery date/C-section date to schedule the newborn infant measurements, ideally before she is discharged.

Study staff will also distribute delivery visit reminder cards at Study Visits 1 and 2 that contain the telephone number to call or text once they go into labor; participants will be instructed to keep this reminder card in their hospital bags.

Study staff will also remain in contact with the UTMC staff in labor and delivery so they are aware that the patient is a study participant and will need newborn infant measurements. Study staff will additionally search the Medical Center's electronic admission system and the labor and delivery patient board for study participants as they near delivery. UTMC staff in labor and delivery and the Mother/Baby Units will also help facilitate scheduling the delivery visit to obtain the newborn measurements.

Newborn measurements will not be taken if the baby is admitted to Neonatal Intensive Care and is critically ill. Measurements will take place only at UTMC or the participants' homes.

First, study staff will weigh the baby (using a portable study scale). Second, study staff will measure the length of the infants (i.e., recumbent length with a portable infantometer). Third, study staff will measure the infant's head, abdominal and arm circumferences (i.e., using a tape measure). Forth, study staff will measure flank, thigh, triceps, bicep and subscapular skinfolds with calipers to assess body composition. The mother can hold the infant during the circumference and skin folds measurements. Although there is no risk of harm from these measures, the baby may briefly experience a very mild discomfort resulting from the light pinch of skin with the caliper (this pinching sensation is about as uncomfortable as if one were to lightly take a pinch of skin between the fingers).

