Due to COVID-19, the Delivery Visit may potentially be canceled.

P. Interventions

The primary goal of the PA intervention is to achieve at least 30 minutes per day of walking/stepping in place. The secondary goal is to use a physical activity tracker to log and track their walking/stepping in place, and to get at least 3,000 steps during their 30 minutes of walking/stepping. The STEP Up intervention will offer a FitBit Charge 3; the devices will be managed by Fitabase so that both the participant and the interventionists will be able to view her Activity Log (i.e., the Fitbit's record of minutes spent walking/stepping and the number of steps obtained during those minutes), and will thus encourage the use of that device. Women randomized to the PA intervention will have an initial video chat (i.e., Zoom) counseling session to discuss exercising safely and exercising safely during pregnancy, go over the STEP Up program goals, set a walking/stepping goal for the following week, and receive and review use of the Fitbit to track progress towards their goal. They will then participate in 4 telephone/video chat sessions to discuss progress towards their walking/stepping goals and receive behavior change counseling to maintain and increase their walking/stepping (i.e., approximately 1 telephone session per week). They will be offered optional maintenance sessions

through delivery, as requested (i.e., approximately weekly). If the participant does not have internet access, the intervention will be delivered entirely by telephone.

Women randomized to the 'Next Steps' intervention will receive information on mom and baby wellness that is unrelated to physical activity, diet, metabolism, or weight (e.g., her own immunization status during pregnancy and encouragement to immunize her baby on schedule, infant car seats & safety checks, contraceptive options and a contraceptive plan), delivered in 5 telephone/video chat sessions (identical to the STEP Up intervention described above) in order to control for contact time. As such, the trial is called Project Wellness and it will be advertised that all study participants will work with a lifestyle coach on wellness.

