**Statistical Analysis Plan date:**

8/8/2023

Analyses will be intention to treat. Mean daily minutes spent in walk/run activity and MVPA (i.e., device-based measures), as well as mean MET hours per week in the sports and exercise domain overall and just walking and jogging (i.e., questionnaire-based measures) will be compared between groups with Proc Mixed in SAS 9.4. All models will be adjusted for GGI vs. GDM status. Models of the device-based measures will include repeated statements for observation day number, by study visit. The model for total MVPA will include additional adjustment for device wear-time (i.e., by day and study visit). Models for the questionnaire-based measures will include repeated statements for study visit. For the neonatal outcomes, PA intervention verse control group differences will be examined in Proc Mixed, adjusting for GGI vs. GDM status.

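### Does a pilot feasibility trial need a named lead outcome and a planned feasibility summary in its SAP?

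*Protocol*

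**What the plan says.** The protocol's title and Section B (Aim) describe the study as a pilot feasibility trial: "To conduct a pilot feasibility RCT among up to 48 women". Section B then states comparative hypotheses on activity, third-trimester glycemic profile and infant anthropometry. It marks only the mediation hypothesis as exploratory.

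Several sections generate feasibility information:

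- **Section M:** "We plan to recruit and enroll up to 48 participants so that we may randomize at least up to 36".
- **Section L:** "Participants will not be randomized until all elements of Study Visit 1 have been completed".
- **Section P:** five sessions per arm, a rule for participants who stop responding, and audio recording of some sessions to check fidelity.
- **Table 1:** acceptance of the interventions, recorded at Study Visit 2.
- **Section O:** an optional newborn visit, with the warning "Due to COVID-19, the Delivery Visit may potentially be canceled".

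The SAP specifies an intention-to-treat analysis. Two device-based and two questionnaire-based activity measures "will be compared between groups with Proc Mixed in SAS 9.4". It continues: "For the neonatal outcomes, PA intervention verse control group differences will be examined in Proc Mixed". It gives no significance level, no order of outcomes and no descriptive table.

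**The concern.** A feasibility pilot is expected to report whether women can be enrolled, randomised, kept in the sessions and measured at follow-up. The SAP paragraph contains only efficacy-type comparisons, so read alone it would deliver none of this.

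It also does not say which comparison leads. The protocol's one use of the word primary that might help is "The primary goal of the PA intervention is to achieve at least 30 minutes per day of walking/stepping in place". That is a target for the participant, not a trial outcome.

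Two things would be at stake. The feasibility question could go unanswered, and one nominally significant result among several unranked comparisons could be presented as a finding when chance explains it equally well.

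**Working it through.** **1. Is there a sample-size or precision figure to reproduce?** No. The ceiling of 48 and the target of 36 come without alpha, power, effect size, SD, dropout rate or precision target. The figures below are illustrations under stated assumptions.

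**2. How many outcomes could be tested?**

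- Activity (SAP): walk/run minutes, MVPA, sports-and-exercise MET-hours, walking-and-jogging MET-hours = 4.
- Neonatal (protocol Sections B and O): weight, length, three circumferences, and "flank, thigh, triceps, bicep and subscapular skinfolds with calipers to assess body composition" = 1 + 1 + 3 + 5 = 10.
- Upper count: 4 + 10 = 14.
- If the five skinfolds feed one body-composition measure: 4 + 6 = 10.
- If only three neonatal outcomes are analysed (illustrative): 4 + 3 = 7.

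Section E of the protocol says four skinfold sites but names five, a clerical slip. With four sites the upper count is 13. The glycemic profile has no model in the SAP paragraph, so it is not counted.

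**3. Chance of at least one false positive.** Assume each outcome is tested at two-sided 5% and there is no true effect. With k independent outcomes the chance is 1 − 0.95^k. Correlation was examined by simulation with 400,000 draws: equicorrelated normal statistics within the activity family and within the neonatal family, with the two families independent of each other.

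| Outcomes | Independent | Correlation 0.3 | 0.5 | 0.7 |
|---|---|---|---|---|
| 4 (activity only) | 1 − 0.95^4 = 0.185 | 0.174 | 0.156 | 0.130 |
| 7 | 1 − 0.95^7 = 0.302 | 0.287 | 0.262 | 0.225 |
| 10 | 1 − 0.95^10 = 0.401 | 0.374 | 0.331 | 0.273 |
| 14 | 1 − 0.95^14 = 0.512 | 0.464 | 0.397 | 0.315 |

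With 13 outcomes the independent figure is 1 − 0.95^13 = 0.487, so the slip over sites makes little difference. The 51% figure needs weight, length, circumferences and skinfolds of the same baby to be independent, which is implausible. The lower figures are the more realistic ones, and all of them apply only if tests at 5% are actually used to make claims.

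**4. What would a feasibility table show at this size?** Exact (Clopper-Pearson) 95% intervals, with assumed retention counts:

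- Randomised of enrolled, 36/48 = 75%: 60% to 86%.
- Retained of randomised, 25/36 = 69%: 52% to 84%.
- Retained of randomised, 29/36 = 81%: 64% to 92%.
- Retained of randomised, 32/36 = 89%: 74% to 97%.

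These describe precision at the planned size. They do not measure any harm from leaving the table out of the SAP. The 36/48 also treats two planning ceilings as if they were an observed yield.

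**5. Setting each gap against what the documents already supply.**

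| Gap in the SAP paragraph | What fills it |
|---|---|
| Enrolled, randomised, retained | Participant-flow counts; no model needed |
| Session completion | Five scheduled sessions per arm (Section P) |
| Acceptance | Collected at Study Visit 2 (Table 1) |
| Delivery-visit completion | Count of optional visits done (Section O) |
| List of neonatal outcomes | Protocol Sections B, E and O |
| Lead comparison | Not stated; only mediation is set apart as exploratory |

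Only the last row is not filled by the protocol or by ordinary reporting. Its consequence depends on confirmatory claims that the SAP does not make.

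**The case for a change.** The strongest case for a change is that a feasibility label should bind the analysis. A flow diagram gives some counts, but it does not define a completed session, valid monitor wear or the scoring of acceptance, and those choices affect the result. Writing them down would cost little. The multiplicity point also does not depend on the uncertain neonatal count, since the four activity measures named in the SAP already give 19% under independence.

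Part of this stands. The SAP paragraph names no lead outcome and no feasibility table, the arithmetic is right, and a few added lines would make the report easier to follow.

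The rest does not compel a change:

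- The Aim states comparative hypotheses and no feasibility endpoint, so the promise is inferred from a label.
- The SAP says outcomes will be compared and examined. It sets no threshold for declaring an effect.
- Making feasibility the main analysis, or making walk/run minutes the lead measure, is a choice on which reasonable statisticians differ. It would also need a check that the device's walk/run category captures stepping in place.
- The SAP is dated 8/8/2023 and the protocol 10/26/2020. The documents do not say when outcome data were seen. A lead measure chosen after that point would carry only post hoc weight.

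**Conclusion.** The observation is accurate for the text available, but it does not call for a change to the plan. It combines missing detail that analysts supply as a matter of course (flow counts, session and visit completion, an outcome list already in the protocol) with a trade-off over whether a small pilot should rank its outcomes. No rule or number in the SAP paragraph is shown to produce a wrong result.

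The size of the multiplicity issue is conditional. It is at most 19% for the four activity measures. For 14 outcomes it is 31% to 46% at within-family correlations of 0.7 to 0.3, with 51% as the ceiling if outcomes are independent or positively correlated. This assumes testing at two-sided 5%, which the documents do not state. The sensible response lies in the report: give the feasibility counts, present group differences as estimates with confidence intervals, and identify any ranking made after outcome data were seen as post hoc.

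The conclusion is limited to the SAP text that could be read. A lead outcome or feasibility summary elsewhere in the SAP would remove the question altogether.

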Surveys (e.g., demographic, health behaviors, medical history, dietary intake) will be administered at baseline (initiated < 30 weeks gestation, Study Visit 1) and at follow-up (initiated < 36 weeks gestation, Study Visit 2); see Table 1 for the variables to be assessed and timing of their assessments. PA will be objectively measured at baseline and follow-up with ActiGraph physical activity monitors (PAMs, i.e., the CentrePoint Insight Watch) worn continuously for 7 days on the dominant wrist. Continuous glucose monitors (CGM) will be worn continuously for 7 days on the participants' non-dominant upper arm (posteriorly located) at Study Visits 1 and 2 to assess maternal glycemic profile (i.e., DEXCOM G6 devices, participants will be blinded to their CGM data). Infant outcomes [i.e., weight; length; head, abdominal and upper mid-arm circumferences; and skinfolds at four sites (flank, thigh, triceps, bicep and subscapular skinfolds)]^{18,64} will be assessed by study staff within 4 days of birth (i.e., the optional delivery visit).

Participants will be randomized to the STEP Up intervention or the Next Steps intervention (described in Section R) once they have successfully completed all of the data assessments for Study Visit 1 (described in Section L). Intervention staff will inform the participants of their program assignment (i.e., STEP Up or Next Steps) and schedule the first intervention session. All intervention sessions will be conducted remotely (i.e., via phone and/or video chat).

Study visits will occur either remotely (i.e., via phone and/or video chat) or take place in private rooms at the UT Medical Center [e.g., a private office or exam room in the High

Risk Obstetrical Consultants (HiROC) clinic or Preston Medical Library; and Labor and Delivery or the Mother/Baby Units on 3 West, 3 East, and 4 West for the delivery visit].

F. Incentives

Participants will receive payments in the amount of: \$80 for Study Visit 1, \$100 for Study Visit 2, and \$100 for the delivery visit (i.e., \$280 total). Incentive payments will be Walmart gift cards distributed either in person, by mail, or dropped off at the participants home upon completion of all of the data assessment elements associated with that Visit. If a gift card is sent by mail and not received, a replacement will be dropped off at the participants home.

G. Parking

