The study will be advertised at local clinics affiliated with the University of Tennessee Medical Center [i.e., who refer patients to HiROC upon GDM diagnosis, specifically: University Women's Specialists, UT Ob/Gyn Center (residents' clinic), and University Midwives]. Posters advertising the study (e.g., women at risk for or with GDM may be eligible, incentive payments will be given for participation, and the study staff's contact information) will be hung in participating the clinics and advertised on their waiting room TV monitors and electronic patient portals, upon receipt of permission from the clinics' leadership. A handout with more details on what participation would entail and the study staff's contact information will also be available at the clinic front desks and in the labs (i.e., where patients are tested for GDM), and will be distributed to potentially eligible patients by clinic staff. Women being referred to HiROC for GDM treatment will be told by the clinic staff that they may be eligible for the study and asked whether they wish to opt out of email, telephone calls and/or text message invitations to learn more about the study. Women who fail the screening test (i.e., 50g, 1-hour OGT) will also be told by clinic staff that they may be eligible for the study and asked if interested or they would like to opt out. Clinic staff will inform study staff of patients opt out/permission to contact status via Message Center (in the EMR) or by email. Those refusing all contact with study staff (i.e., opt outs) will be excluded from the procedures below.

I. Eligibility

Women will be recruited from four clinics associated with the UT Medical Center (listed in Section J); all of these clinics have electronic medical record systems or are soon transitioning to electronic medical record systems that will be used to confirm patient eligibility (i.e., paper charts will be used in the interim, as needed). Study staff will pre-screen the electronic medical records of women diagnosed with GDM who have not refused/opted out of contact with study staff. They will summarize their findings for the physician approvers (e.g., Drs. [name] and [name]). The physician approvers will review these findings and the medical records before signing off on the physician approval to contact forms confirming the patient meets the primary eligibility criteria; at this point, a

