Project Wellness study ID number will be assigned. Study staff will follow up with potentially eligible patients by email, telephone and/or text messages to distribute information about the study and evaluate the secondary eligibility criteria. Staff will arrange by telephone, email, and/or text message to meet eligible and interested women by Zoom or at UTMC.

Primary Eligibility Criteria, Evaluated at the Physician Screening

- Age 18-40 years
- Not previously diagnosed with diabetes (i.e., Type I or Type II diabetes) outside of pregnancy
- Singleton viable pregnancy with low suspicion for clinically significant abnormality or aneuploidy
- Diagnosed with GDM after 24 weeks by:
 - One step diagnostic procedure⁶⁵
- 75-g OGTT after an overnight fast, with plasma glucose measured fasting and at 1 and 2 hrs, and any of the following plasma glucose values are met or exceeded:
 - Fasting: 92 mg/dL (5.1 mmol/L)
 - 1 hr: 180 mg/dL (10.0 mmol/L)
 - 2 hr: 153 mg/dL (8.5 mmol/L)
 - For the Two step diagnostic procedure,^{65,66} only Step 1 (i.e., at risk for GDM) is required for eligibility:
- Step 1: 50-g GLT (non-fasting), with plasma glucose measured at 1 hr \geq 130 mg/dL
 - Any other abnormal value on oral glucose tolerance testing associated with macrosomia⁴²
- No contraindications to exercise (i.e., no absolute contraindications according to published recommendations for exercise during pregnancy⁶⁷), as follows:
 - Hemodynamically significant heart disease
 - Restrictive lung disease
 - Incompetent cervix/cerclage
 - Persistent second or third trimester bleeding
 - Placenta previa or vasa previa after 26 weeks gestation

- Premature labor during the current pregnancy
- Confirmed ruptured membranes
- Preeclampsia/pregnancy-induced hypertension
- Currently non-smoker
- No current illicit drug use
- No current use of daily medications known to alter insulin resistance and metabolic profiles (e.g., metformin, corticosteroids, anti-psychotics)
- Not currently taking medication for polycystic ovarian syndrome (PCOS) (i.e., history of PCOS okay as long as she is not *currently* taking medication for PCOS)
- English speaker and comfortable completing surveys in English (i.e., no translator needed)

Secondary Eligibility Criteria, Evaluated by Study Staff during Recruitment

- Planning/likely to stay in Knoxville through baby's 1st birthday

J. Recruitment Clinics

University Women's Specialists:

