<https://www.utmedicalcenter.org/medical-care/specialty-practices/university-womens-specialists/>

UT Ob/Gyn Center:

<https://utimobgyncenter.utmck.edu/portal/ut-obgyn-center/default.aspx>

University Midwives:

<https://www.utmedicalcenter.org/medical-care/specialty-practices/university-midwives/>

Women's Care Group:

<https://www.utmedicalcenter.org/medical-care/medical-services/specialty-practices/womens-care-group-knoxville/>

K. Recruitment at HiROC

Study staff will also work with HiROC on study recruitment. HiROC clinic staff (e.g., diabetes educators) will also mention the study to potentially eligible women upon their referral to HiROC for GDM, and those who do not refuse/opt out of receiving more information about the study will be referred to study staff for follow-up. Study staff will pre-screen the medical records and summarize their findings for the physician approvers. Physician approvers will review their findings and the medical records before signing off on the physician approval to contact form; at this point, a Project Wellness study ID number will be assigned. Study staff will follow up with potentially eligible patients by email, telephone and/or text messages to distribute information about the study and evaluate the secondary eligibility criteria. Staff will arrange by telephone, email, and/or text message to connect with eligible and interested women for their Study Visit 1. Study staff will call, email, and/or text the participant to remind her of the scheduled day/time/modality (i.e., remote or in-person at UTMC) of her Study Visit 1.

L. Study Visit 1 (Baseline data assessment, scheduling initiated at after 24 weeks and Study Visit ≤ 30 weeks gestation)

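### Absolute contraindications to exercise are checked once, at a chart sign-off before contact and consent, with no stated re-check before allocation to the walking arm

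*Protocol*

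**What the plan says.** Section I of the Protocol divides eligibility into primary and secondary criteria. The absence of absolute contraindications to exercise is a primary criterion, under the heading "Primary Eligibility Criteria, Evaluated at the Physician Screening". Eight conditions follow, one of them tied to gestation: "Placenta previa or vasa previa after 26 weeks gestation".

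The screening is a review of the medical record. Study staff summarise the chart, and the physician approvers look at the summary and the record before "signing off on the physician approval to contact forms confirming the patient meets the primary eligibility criteria". Section K gives the same order for women referred to HiROC: findings and records are reviewed "before signing off on the physician approval to contact form". Study staff then approach the woman and assess only the secondary criterion, which is whether she expects to stay in Knoxville. Consent is taken later, at Study Visit 1 (Section L).

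Section E has participants randomised "once they have successfully completed all of the data assessments for Study Visit 1". Section L lists what that covers (surveys, food questionnaire, activity monitor, diary log, glucose monitor) and sets the deadline: "These elements must be completed and received by 30 weeks 6 days gestation in order to be randomized". Section M then has intervention staff "schedule the initial intervention session (at < 31 weeks 6 days gestation"). Section P says the opening STEP Up session will "discuss exercising safely and exercising safely during pregnancy, go over the STEP Up program goals, set a walking/stepping goal" for the coming week.

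**The concern.** Several of the listed conditions are events of later pregnancy, so a woman who is clear at sign-off may not be clear at allocation. The stated conditions for randomisation concern completeness of data only. A woman who has developed a listed condition since sign-off can meet all of them and be assigned a daily walking goal that the protocol's own exclusion list says she should not have.

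What is at stake is participant safety. The effect on validity is small: a re-check would remove only conditions already present at allocation. Conditions that develop afterwards rightly stay in the intention-to-treat analysis that the SAP specifies.

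**Working it through.** The documents give no figure to reproduce here. The check has three parts: the order of events, the length of the gap, and which listed conditions can arise within it.

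**Order of events**

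1. Chart review and physician sign-off on all primary criteria (Sections I and K).
2. Contact by study staff, who assess the secondary criterion only (Sections I and K).
3. Consent and start of Visit 1 (Section L).
4. Seven days of activity-monitor and glucose-monitor wear; materials returned (Sections E and L).
5. Randomisation (Section M).
6. First intervention session (Sections M and P).

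The contraindication list is applied at step 1. The nearest later items are these:

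- Table 1 marks medical history in a column shared by the physician screen and Visit 1. No text compares the answers with the list or withholds allocation because of them.
- The safety discussion is at step 6, after allocation.
- Adverse events are marked only at Visit 2.

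**Length of the gap**

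Gestational age in days is 7 × weeks + days:

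- 24w0d = 7 × 24 = 168
- 28w0d = 7 × 28 = 196
- 30w6d (materials deadline, Section L) = 7 × 30 + 6 = 216
- 31w6d (latest first session, Section P) = 7 × 31 + 6 = 223

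The minimum gap from sign-off to randomisation is about 7 days, because full device wear falls between them. The maximum depends on the sign-off date, which the protocol does not fix. Two dates are assumed to show the range:

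| Assumed sign-off | To materials deadline | To latest first session |
|---|---|---|
| 24w0d | 216 − 168 = 48 days | 223 − 168 = 55 days |
| 28w0d | 216 − 196 = 20 days | 223 − 196 = 27 days |

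From the materials deadline to the latest first session is 223 − 216 = 7 days. Section P allows the session on 31w6d itself. Section M writes a strict less-than sign, which would shorten the 55, 27 and 7 by one day each.

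**Conditions that can change within the gap**

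Of the eight listed, at least four can newly arise: persistent second- or third-trimester bleeding, premature labor, ruptured membranes, and preeclampsia or pregnancy-induced hypertension. Previa makes five if sign-off comes before 26 weeks, because the criterion cannot be met until then. The documents give no incidence for any of these, and none is assumed, so no expected number of affected women is calculated.

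**The case against.** The strongest reply is that the criteria do not lapse once evaluated. A woman known at Visit 1 to have preeclampsia does not satisfy Section I, and the baseline survey collects medical history that must be received before randomisation. On this view the plan lacks only an explicit instruction to act on new information. That is fair as to what a careful team would do, but no stated step has anyone look, and no stated route carries a new clinic diagnosis to study staff before allocation.

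Second, allocation is not exposure. No walking goal exists until the first STEP Up session, which covers exercising safely. A contraindication screen at that session would protect her as well. But the session is described as counselling and is not tied to the list.

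Third, other safeguards exist. Women with GDM attend HiROC weekly to bimonthly (Section D), at-risk women remain under the Section J clinics, and the activity is moderate walking with a talk test (Section A). These lower the risk. None of them applies the list before allocation.

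Fourth, a single re-check does nothing for conditions that appear later, although sessions run to 36w6d and maintenance can continue to delivery. This stands, and it is why a pause rule is also worth having. The consent pages and workbooks are not available and may carry such advice, so the lack of that rule in the visible text is a lesser point. Advice to participants would still not replace a check before allocation.

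Finally, 48 and 55 days are ceilings. They combine the earliest plausible sign-off with the last permitted day, and no typical gap can be derived.

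**Conclusion.** The concern holds. The protocol's stated timing leaves at least about 7 days, and possibly several weeks, between the only contraindication check and allocation. At least four of the eight listed conditions can arise in that time, or five with previa. The upper end (48 days to the materials deadline, 55 to the latest first session) rests on an assumed sign-off at 24w0d. At 28w0d the figures are 20 and 27. How many women would be affected cannot be estimated from the documents.

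This should be fixed because it is a cheap gain in safety. It is not a fatal flaw: other care lowers the risk, and the analysis and its interpretation barely change. The conclusion rests on the visible text. A re-check described only in removed pages cannot be excluded.

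**What to change.** In Section M, require the physician approver to re-confirm the Section I contraindication list from the current chart, with a date, after the Visit 1 materials are received and before the allocation is released. Because this precedes allocation, it leaves concealment and intention-to-treat intact.

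As a secondary addition to Section P, state that STEP Up walking goals are paused and the participant is referred to the study physician if she reports a listed condition or a clinician has told her to stop exercising. She would still complete Visit 2 and stay in the analysis. No exercise question should be added to the Next Steps calls, whose content is deliberately kept away from physical activity.

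The cost is one more chart look per woman by approvers who already review these records, at most 48 given the enrolment cap. A few enrolled women may be excluded before randomisation, and STEP Up coaches need brief training on the pause rule. The timetable allows it, though it is tight at the end: materials arriving on the 30w6d deadline leave up to 7 days before the latest first session (6 under Section M's wording), and those days must also cover allocation, contact and scheduling.
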